3.2 Exclusion Criteria

Create a numbered list of the exclusion criteria that define who will be excluded in your study.

- Diagnosis of intellectual disability
- History of known genetic or neurologic disease
- Need for treatment with opioid painkillers
- Weight <25kg
- Inability to swallow pills
- Lack of proficiency in written or spoken English
- Urine drug screen positive for opioids at enrollment
- Positive serum pregnancy test at enrollment
- Lactation
- Elevation of three times the upper limit of normal for age in either alanine aminotransferase (ALT) or asparagine aminotransferase (AST).
- High risk of suicide at enrollment on Columbia Suicide Severity Rating Scale (C-SSRS, for participants age 18)²⁰ or Ask Suicide Screening Questions (ASQ, participants age 13 to 17)²¹
- Current Naltrexone use

3.3 Early Withdrawal of Subjects

3.3.1 Criteria for removal from study

Insert subject withdrawal criteria (e.g., safety reasons, failure of subject to adhere to protocol requirements, subject consent withdrawal, disease progression, etc.).

- New need for medical hospitalization for malnutrition or eating disorder
- Need for escalation of level of care for eating disorder, that is, requirement for inpatient or residential-level eating disorder care
- New need for opioid painkillers
- Subject consent withdrawal
- Inability to adhere to protocol requirements
- New diagnosis of pregnancy
- New elevation of three times the upper limit of normal for age in either alanine aminotransferase (ALT) or asparagine aminotransferase (AST).

3.3.2 Follow-up for withdrawn subjects

Describe when and how to withdraw subjects from the study; the type and timing of the data to be collected for withdrawal of subjects; whether and how subjects are to be replaced; the follow-up for subjects withdrawn from investigational treatment.

- Patients who are withdrawn from the study will continue with their routine eating disorder
 care at whatever level of care is clinically appropriate for them at that time; that is, they will
 continue with routine care. Data generated from their participation in this study will be used
 to the point of their withdrawal. Specific study subjects do not require replacement.
- Patients who screen positive for opioid substances at enrollment will be provided with a referral for substance use disorder treatment.
- Patients who screen positive for pregnancy will be referred for pregnancy options counseling.

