1.3 Secondary Study Endpoints

State the secondary endpoints to be measured in the study.

Secondary outcomes will include improvement in scores on Eating Disorder Examination Questionnaire (EDE-Q)², the Patient Health Questionnaire-9 scale (PHQ-9,, a measure of depression)³ the Generalized Anxiety Disorder-7 scale(GAD-7, an inventory of anxiety)⁴, Alexian Brothers Urge to Self-Injure Scale (ABUSI; an inventory measuring the desire to self-harm)⁵, and Behavioral Inhibition System/Behavioral Activation System score (BIS/BAS; an impulsivity inventory)⁶; need for escalation of level of care (such as requirement for early termination of partial hospitalization program to attend inpatient or residential eating disorder care or hospitalization for medical stabilization); and rate of weight restoration.

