The subject will be provided with oral naltrexone or placebo weekly from the MSHMC research pharmacy. Subjects will be given one weeks' worth of medication at a time. Subjects will be randomized at enrollment to receive either study drug (naltrexone) or placebo. Participants or parents of minor participants will be provided study drug or placebo following completion of urine drug screen and consent/assent. Patients will take the medication daily while they are in programming; after completion of programming or withdrawal from the study they will no longer be given study medication. For subjects who are enrolled in child PHP and who eat meals with parents, the families may choose to administer study drug during meals at programming. For adult patients enrolled in adult programming, subjects may choose to self-administer the medication.

On their first contact with PHP, all patients in Adult PHP complete various eating disorder indices as a part of routine care, including the ED-15, PHQ-9, GAD-7, and EDE-Q. This battery of indices is repeated every 3 weeks while a patient is in programming.

For those who are enrolled in this study, they will complete their routine indices, in addition they will also complete the BIS/BAS and the ABUSI at enrollment and at weeks 1, 3, and 6 while enrolled in the study. Participants will also be asked to take the routine indices (ED-15, EDE-Q, PHQ, GAD, BIS/BAS, and ABUSI) at week 8 or 9 for a post-treatment evaluation. These will be taken in an in-person medical appointment or electronically via RedCap

6 months after enrollment, subjects will be sent copies of ED-15, EDE-Q, PHQ, GAD, BIS/BAS, and ABUSI indices either in an in-person medical appointment or via RedCap to complete. If the patient returns for medical follow-up between 5 and 7 months after enrollment, their height, weight, and body mass index will also be recorded to determine if weight restoration was maintained.

Patients in Child PHP typically complete a different inventory every three weeks as part of routine care. If a patient choses to participate in this study they will be asked to complete the same surveys as participants in Adult PHP (ED-15, GAD-7, and PHQ-9), and they will receive the same amount and type of compensation as those who already take them as part of standard of care.

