REDCap, will be used to store the surveys. Participants will be sent the link to the battery of surveys via email at the designated times listed above. The link will redirect them to the programmed surveys in REDCap. Their responses will be stored in REDCap until data is exported and stored on the secure file server (hersheymed.net/files). Only authorized study personnel will have access to the REDCap surveys and folder access on the secure network.

At initial contact with the eating disorders clinic, all patients receive an initial battery of laboratory tests as a part of the standard of care for eating disorder. These tests include liver function assays and transaminase levels. Further information about liver function test and monitoring for drug-induced liver injury is outlined in section 9.0.

7.1.1 Enrollment.

Provide a description of what procedures will be performed on visit 1 or day 1 or pre-test in order of how these will be done. If your study only involves one session or visit, use this section only and indicate 7.2.2 as not applicable.

As discussed above, patients can be enrolled at either their initial medical or initial psychiatric appointments for participation in the appropriate PHP for eating disorder.Per Joint Commission regulations of partial hospitalization programs for any psychiatric diagnosis, a complete blood count, blood chemistry, liver function test, urinalysis, and electrocardiogram must be obtained at enrollment and other studies at the program's discretion. If all necessary bloodwork, EKG, and urine studies have been obtained within the last two weeks, these results will be tracked down, recorded into the medical record, and any necessary and routine studies that have not been completed prior to this appointment will be completed at enrollment.

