7.3.2 Treatment Regimen

Describe dose, route of administration and treatment duration. Include information about dose adjustments.

All subjects receiving study medication will receive oral naltrexone 50mg oral tablets, blinded as described above. All subjects receiving placebo will receive methylcellulose, blinded as described above. All capsules, regardless of contents, will be administered by mouth once daily, at a time of day to be chosen by the study participant.

In pediatric autism literature, doses between 0.5-2 mg/kg are described^{8,11,22,22-25}, though in adult eating disorder literature doses of 50-100mg are described^{13,14,16-18}. Food and Drug Administration labelling of oral naltrexone for treatment of alcohol use disorder and opioid receptor blockade describe an appropriate maintenance dose of 50mg per day⁷. Therefore subjects will receive 50mg of oral naltrexone a day if they are randomized to the medication group. Patients with body weight less than 25kg are excluded from the study so that no participant will exceed the maximum described pediatric dose of 2 mg/kg. Participants receiving

study article will receive 25mg of naltrexone for three days, followed by increase to study dose of 50mg/day The maximum daily dose is 50mg.

Participants will take study medication daily while they are in PHP or for six weeks total. That is, if a participant is in PHP for three weeks, they will take the study medication for the entirety of their time in PHP and then continue to take the medication for three additional weeks after discharge from PHP. If a participant is in PHP for twelve weeks—which is quite uncommon—they will only take study medication for six weeks.

For participants who complete PHP early, they will be asked to complete the same battery of surveys at 3 and 6 weeks, at weeks 8/9 for post-treatment evaluation, and at 6 months. Survey responses will be obtained via RedCAP for participants not on-site at time of survey completion.

Participants who, upon completion of the study, feel that they had significant benefit from the study article which lost upon withdrawal of the study article, are eligible for open label oral naltrexone therapy if desired. Participants will be asked at subsequent medical and behavioral health follow-up appointments if they felt they benefitted from the study article. If they feel they did, they will be offered a prescription for oral naltrexone to start at 25mg/day for three days and then 50mg a day after.

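### No ED-15 score is planned after removal for eating-disorder hospitalisation or escalation of care, so the comparison between arms can be biased

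*Combined protocol and SAP*

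**What the plan says.** Section 3.3.1 is a list of reasons for removal from the study. Besides medical hospitalisation for malnutrition or eating disorder, it includes "Need for escalation of level of care for eating disorder, that is, requirement for inpatient or residential-level eating disorder care". Section 1.3 makes the same event a secondary endpoint: "need for escalation of level of care (such as requirement for early termination of partial hospitalization program".

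For those removed, section 3.3.2 says "Data generated from their participation in this study will be used" "to the point of their withdrawal", that they continue in routine care, and that they need not be replaced. The template prompt above that answer asks for "the type and timing of the data to be collected for withdrawal of subjects"; the answer gives neither.

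Remote collection exists for participants in general. Section 7.2 (Study Procedures) says "6 months after enrollment, subjects will be sent copies of ED-15" and "Participants will be sent the link to the battery of surveys via email at the designated times listed above". Section 7.3.2 adds "Survey responses will be obtained via RedCAP for participants not on-site at time of survey completion", in a paragraph about people who finish the partial hospitalisation programme (PHP) early. Section 19.1.1 describes emailed surveys at six weeks for those who have completed PHP, and at six months. None of these places says that removed participants stay on the surveys, and section 13.0 limits anyone who withdraws to the enrolment payment.

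Section 8.3 compares outcomes at three weeks, six weeks and six months. It names no analysis set, model or missing-data method. For the outcomes it points to 1.1 and 1.2, which may be a numbering slip but does not reach escalation in 1.3.

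**The concern.** The two removal triggers are deterioration of the illness that ED-15 measures, so scores would go missing because they are likely to be bad. If naltrexone prevents deterioration, placebo loses more of its worst scores and the observed difference shrinks. If outcome-related removals are more frequent on drug, naltrexone looks better than it is. The second route is open because section 10.0 withdraws participants with severe low appetite, self-injury or depression, and section 19.1.2 withdraws those with harm probably related to study article.

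A likelihood-based model corrects only for what earlier scores reveal. A score that was never collected cannot be recovered at analysis, so this has to be settled in the protocol.

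**Working it through.** **Inputs.** From the documents: 30 per arm (8.1). Section 8.2 bases the number on feasibility and gives no effect size, SD, power or dropout rate, so there is no figure to reproduce. Assumed: ED-15 at week 6 scaled to SD 1, with lower scores better; a t-test on those not removed; removal when a latent severity L exceeds a cut-off, where L has correlation ρ with ED-15.

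**A. True effect of 0.50 SD, 20% of placebo removed.** With Y the ED-15 score, L = ρY + √(1−ρ²)e, and removal occurs if L > c = 0.842, the 80th normal percentile.

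- Placebo mean among those retained: −ρ·φ(c)/Φ(c), where φ(c)/Φ(c) = 0.350.
- Drug removal: 1 − Φ(c + 0.5ρ). Drug mean among those retained: −0.5 − ρ·φ(c + 0.5ρ)/Φ(c + 0.5ρ).
- At ρ = 0.5: placebo −0.5 × 0.350 = −0.175. Drug cut-off 1.092, removal 13.7%, mean −0.5 − 0.5 × 0.255 = −0.627. Difference 0.452.

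| ρ | Removed on drug | Difference among retained (SD) | Shrinkage | Power |
|---|---|---|---|---|
| 0.2 | 17.3% | 0.492 | 1.6% | 39.6% |
| 0.3 | 16.1% | 0.482 | 3.6% | 39.2% |
| 0.5 | 13.7% | 0.452 | 9.5% | 37.6% |
| 0.7 | 11.7% | 0.410 | 17.9% | 35.0% |
| 0.9 | 9.8% | 0.358 | 28.4% | 31.4% |

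Power with no loss is 47.8%. Losing the same numbers at random gives 40.2 to 41.6%, so at ρ = 0.2 nearly all of the power loss comes from smaller numbers, not bias. Shrinkage is 1.1 to 18.4% with 10% of placebo removed, and 2.0 to 35.9% with 30%.

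**B. No true effect, 10% removed on placebo and 25% on drug, all outcome-related.** Spurious benefit = ρ × [φ(a₁)/Φ(a₁) − φ(a₀)/Φ(a₀)] = ρ × (0.424 − 0.195) = 0.229ρ, where a₁ and a₀ are the 75th and 90th normal percentiles. At ρ = 0.2, 0.3, 0.5 and 0.7 this is 0.046, 0.069, 0.114 and 0.160 SD. Simulated two-sided rejection at ρ = 0.2, 0.5 and 0.7 is 5.1, 6.8 and 9.2%. If only half of the excess is outcome-related (17.5% against 10%), the benefit is ρ × (0.312 − 0.195), or 0.023 to 0.082 SD; if none is, it is zero. For scale, the standard error of the difference at 30 per arm is √(2/30) = 0.26 SD.

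**C. Can a model repair it?** Large simulations used a week 3 to week 6 correlation of 0.6 to 0.7 and a regression of week 6 on week 3 averaged over everyone randomised, with ρ from 0.2 to 0.9 in A and 0.2 to 0.7 in B.

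| Removal driven by | Analysis | A (truth 0.50) | B (truth 0) |
|---|---|---|---|
| Observed week 3 score | Completers | 0.50–0.44 | 0.03–0.11 |
| Observed week 3 score | Model | 0.50 | 0.00 |
| Unobserved week 6 score | Model | 0.50–0.39 | 0.02–0.12 |

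**The case against.** - **The text does not forbid later collection.** Section 3.3.2 keeps earlier data and is silent on later data; the six-month mailing in 7.2 goes to subjects without condition; 7.1.2 arranges a no-cost six-month visit. This stands as a real ambiguity at six months, although 3.3.2 and 13.0 point the other way. It does not help at weeks 3 and 6.
- **The completers' t-test is assumed, not planned.** True: 8.3 names no test, and a suitable model removes the bias if removal follows an observed score. Part of the exposure therefore comes from the silence of 8.3. The rest, where removal follows the missing score, does not.
- **Collecting the scores changes the quantity estimated.** Inpatient or residential care may itself lower ED-15. If it does so by X SD, the all-randomised difference in A becomes 0.50 − X × (0.20 − drug removal). At ρ = 0.5 and X = 1 that is 0.50 − 0.063 = 0.44, slightly below the completers' 0.45. The two are equal at X = 0.30, 0.45, 0.76, 1.07 and 1.40 SD for ρ = 0.2, 0.3, 0.5, 0.7 and 0.9. This stands: the shrinkage in A is not an amount the fix gives back. What the fix gives is a comparison of the groups as randomised. Non-response among the sickest could still leave some bias.
- **Scenario B is speculative and this is a pilot.** Section 2.1 describes the drug as well tolerated, and 10.0 withdraws only for severe effects. That limits the likely size. But section 1.2 makes a statistically significant ED-15 difference the primary outcome, so the direction of error matters even with 60 participants.
- **Escalation is still monitored (9.2).** So the event is recorded, but recording it does not supply the missing ED-15 score.

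**Conclusion.** The concern holds. Read as written, the plan removes participants for worsening of the illness under study and provides for no further ED-15 score from them. The comparison can be biased in either direction. Bias requires removal to be related to ED-15 and to differ between arms in rate or mechanism; removals unrelated to ED-15, such as opioid need after an accident, mainly cost precision.

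Its size cannot be determined from the documents. Under the stated assumptions it runs from negligible, when removal is weakly related to ED-15, to about 28% of a 0.50 SD effect at 20% placebo removal, or a false benefit of up to 0.16 SD when drug removals are more frequent. Both are smaller than the standard error of 0.26 SD. The case for acting rests on the low cost and the irrecoverability of the data rather than on a large expected bias. Confidence is moderate, because the six-month provision can be read either way.

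**What to change.** Leave the criteria for stopping study article as they are, and separate them from leaving the study.

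- **3.3.2:** replace the rule on data use with a statement that every randomised participant who has not withdrawn consent to data collection is sent the REDCap battery at weeks 3, 6 and 8/9 and at six months, whatever their treatment or level of care.
- **8.3:** analyse all randomised participants in their assigned arm with a repeated-measures model using every available ED-15 score (7.1 also schedules enrolment and week 1). Extend the cross-reference to 1.3 so that escalation is compared by arm.
- **Optional:** add a sensitivity analysis that ranks escalated participants with no score as worst, and pay the six-month card to anyone who completes that assessment.

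The cost is protocol and consent wording plus a few more surveys by a route already in place. The real downside is that some scores will be taken off drug or during inpatient or residential care, so the estimate includes the effect of that care and need not equal the on-drug effect. The protocol should say so.

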4.0 Recruitment Methods

- Upload recruitment materials for your study in CATS IRB (http://irb.psu.edu). **DO NOT** include the actual recruitment wording in this protocol.
- StudyFinder: If StudyFinder (http://studyfinder.psu.edu) is to be used for recruitment purposes, separate recruitment documents do not need to be uploaded in CATS IRB. The necessary information will be captured from the StudyFinder page in your CATS IRB study.
- Any eligibility screening questions (verbal/phone scripts, email, etc.) used when contacting potential participants must be uploaded to your study in CATS IRB (http://irb.psu.edu).

[Do not type here]

4.1 Identification of subjects

Describe the source of subjects and the methods that will be used to identify potential subjects (e.g., organizational listservs, established recruitment databases, subject pools, medical or school records, interactions during a clinic visit, etc.). If not recruiting subjects directly (e.g., database query for eligible records or samples) state what will be queried, how and by whom.

StudyFinder:

o If you intend to use StudyFinder (http://studyfinder.psu.edu) for recruitment purposes, include this method in this section.

o Information provided in this protocol needs to be consistent with information provided on the StudyFinder page in your CATS IRB study.

For Penn State Health submissions using Enterprise Information Management (EIM) for recruitment, and for non-Hershey locations as applicable, attach your EIM Design Specification form on in CATS IRB (http://irb.psu.edu). See "HRP-103- Investigator Manual, What is appropriate for study recruitment?" for additional information. **DO NOT** include the actual recruitment material or wording in this protocol.

We will identify potential subjects in the Adolescent Medicine and Eating Disorders Clinic at Milton S. Hershey Medical Center. Potentially eligible participants are adolescents and young adults coming to their initial medical assessment for eating disorder evaluation. Patients who elect to attend either the child or adult Partial Hospitalization Program for Eating Disorders (PHP) who are also medically appropriate for this level of care between ages 13-25 (inclusive) will be approached at their intake appointment for recruitment and consent.

4.2 Recruitment process

Describe how potential subjects first learn about this research opportunity or indicate as not applicable if subjects will not be prospectively recruited to participant in the research. Subject recruitment can involve various methods (e.g., approaching potential subjects in person, contacting potential subjects via email, letters, telephone, ResearchMatch, or advertising to a general public via flyers, websites, StudyFinder, newspaper, television, and radio etc.). **DO NOT** include the actual recruitment material or wording in this protocol.

[Do not type here]

4.2.1 How potential subjects will be recruited.

Potential subjects will be approached at their intake appointment or at initial psychiatry appointment for child or adult partial hospitalization program (PHP) for eating disorder, if this is the level of care they have elected to pursue. The study will be explained to them at that time and consent will be obtained, should the potential subject wish to enroll. As all participants in the study are also participating in a higher level of care for eating disorder through MSHMC, all participants are patients of either [name] or [name], who are both study team members.

4.2.2 Where potential subjects will be recruited.

Potential subjects will be recruited in a private therapy or medical room at the Adolescent Medicine and Eating Disorders Clinic on the second floor of the Briarcrest building.

4.2.3 When potential subjects will be recruited.

Potential subjects will be enrolled at one of two times: either at the initial medical screening appointment after the decision has been made for the patient to enroll in PHP, or at the initial psychiatry appointment following initial medical appointment (that is, at actual enrollment in programming).

4.2.4 Describe the eligibility screening process and indicate whether the screening process will occur before or after obtaining informed consent. Screening begins when the investigator obtains information about or from a prospective participant in order to determine their eligibility. In some studies, these procedures may not take place unless HIPAA Authorization is obtained OR a waiver of HIPAA Authorization when applicable for the screening procedures

is approved by the IRB. [For FDA regulated studies, consent for any screening activities would need to be obtained prior to screening unless specifically waived by the IRB.]

When patients come into the clinic for either an initial medical screening appointment for their enrollment in PHP or in the initial psychiatry appointment that they have when they enroll, a staff member will assess the patient's eligibility in participating in the research study using the information in the patient's chart and information that is obtained in the appointment. The primary screening criterion will be that the potential subject choses to enroll. Potential subjects who are not medically appropriate for PHP or who do not desire to attend PHP will not be screened any further for the purposes of this study. The only screening that must take place is a point-of-care pregnancy test for postmenarchal (having had at least one menstrual cycle) females with amenorrhea (absent or missed menses)—which is standard of care for these patients regardless of their decision to enroll or not—and a urine drug screen, as oral naltrexone may cause immediate opioid withdrawal if administered to a person with opioid-positive urine. Potential subjects with a positive urine pregnancy test or urine drug screen positive for opioids will not be enrolled. Urine drug screen and urine pregnancy test are specifically outlined in the study consent document.

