3.1 Inclusion Criteria

Create a numbered list of the inclusion criteria that define who will be included in your final study sample (e.g., age, gender, condition, etc.)

- Ages 13-25 (inclusive)
- Any sex
- Diagnoses of anorexia nervosa binge-purge subtype, bulimia nervosa, purging disorder, or atypical anorexia nervosa with bingeing or purging behaviors according to the Diagnostic and Statistical Manual version 5 diagnostic criteria
- Electing to participate in child or adult partial hospitalization program for eating disorder treatment at MSHMC
- The diagnostic criteria for anorexia nervosa, binge-purge subtype, are:
 - A. Restriction of energy intake relative to requirements, leading to a significantly low body weight in the context of age, sex, developmental trajectory, and physical health.

- Significantly low weight is defined as a weight that is less than minimally normal or, for children and adolescents, less than minimally expected.
- B. Intense fear of gaining weight or of becoming fat, or persistent behavior that interferes with weight gain, even though at a significantly low weight.
- C. Disturbance in the way in which one's body weight or shape is experienced, undue influence of body weight or shape on self-evaluation, or persistent lack of recognition of the seriousness of the current low body weight
- D. During the last three months the individual has engaged in recurrent episodes of binge eating or purging behaviour (i.e. self-induced vomiting, or the misuse of laxatives, diuretics, or enemas).¹⁹
- E. A diagnosis of atypical anorexia nervosa can be made when the body weight is normal or high If these patients engage in bingeing or purging behaviors as defined in anorexia nervosa, binge-purge subtype, they are eligible for inclusion in this study
- The diagnostic criteria for bulimia nervosa are:
 - A. Recurrent episodes of binge eating. An episode of binge eating is characterized by
 - B. both:
 - i. Eating in a discrete period of time (e.g. within any 2 hour period), an amount of food that is definitely larger than what most individuals would eat in a similar period of time under similar circumstances;
 - ii. A sense of lack of control over eating during the episodes (e.g. a feeling that one cannot stop eating or control what or how much one is eating.

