5.2 Obtaining Informed Consent

5.2.1 Timing and Location of Consent

Describe where and when the consent process will take place.

Consent and assent will take place at recruitment. Potential subjects will be recruited and enrolled at the completion of either their medical intake appointment for PHP or following the completion of their first psychiatry appointment on their first day of PHP. This will take place in a private therapy or medical room in the Adolescent Medicine and Eating Disorders Clinic, on the 2nd floor of the Briarcrest building.

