7.2 Study Procedures

Provide a step by step description of all research procedures being conducted (broken down by visit, if applicable) including such information as below (where and when applicable); describe the following:

- HOW: (e.g., data collection via interviews, focus groups, forms such as surveys and questionnaires, medical/school records, audio/video/digital recordings, photographs, EKG procedures, MRI, mobile devices such as electronic tablets/cell phones, observations, collection of specimens, experimental drug/device testing, manipulation of behavior/use of deception, computer games, etc.)
- WHERE: (e.g., classrooms, labs, internet/online, places of business, medical settings, public spaces, etc.)

Subjects participating in this study will receive routine care for eating disorder at a partial hospitalization (PHP) level of care at MSHMC. In PHP, all patients have biweekly medical screening visits for the duration of their time in care, as well as weekly individual therapy sessions, individual dietician sessions, and psychiatry appointments. They have supervised meals and numerous group therapy sessions. Every three weeks, patients in PHP complete a battery of mood and eating disorder indices including those evaluated in this study; participants in this study will complete an additional two surveys with this routine battery. Participants in this study will have no alterations in their routine eating disorder care outside of study article use and these additional surveys.

Subjects will be enrolled at their first visit for eating disorder programming at child or adult partial hospitalization (PHP) programming at MSHMC adolescent medicine eating disorders clinic. Informed consent/assent will be obtained as described above.

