7.3.3 Method for Assigning Subject to Treatment Groups

Describe the randomization process and how the associated treatment assignment will be made.

Subjects will be randomized at enrollment using RedCap. Randomization will be stratified by age (16 and under or 17 and older) and diagnosis (anorexia nervosa binge/purge subtype and bulimia nervosa or OSFED with bingeing or purging behaviors), equaling 4 strata.

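### The protocol gives conflicting times for enrollment, so a person can be randomized before PHP starts and the baseline ED-15 has no uniform time zero

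*Combined protocol and SAP*

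**What the plan says.** **When enrollment happens.** Section 4.2.3 gives two times. One is the medical intake visit: "Potential subjects will be enrolled at one of two times: either at the initial medical screening appointment after the decision has been made" to enter PHP. The other is the first psychiatry appointment, which section 5.2.1 describes as "following the completion of their first psychiatry appointment on their first day of PHP". Section 7.1.1 repeats that "patients can be enrolled at either their initial medical or initial psychiatric appointments".

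Section 7.2 (Study Procedures) gives only one time: "Subjects will be enrolled at their first visit for eating disorder programming". The later section on Duration of Participation also starts the six-month study period at enrollment in PHP.

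**What depends on enrollment.** Section 7.3.3: "Subjects will be randomized at enrollment using RedCap". The schedule of events in section 7.1 puts the first ED-15, EDE-Q, ABUSI, GAD-7, PHQ-9 and BIS/BAS in the Enrollment column. Section 7.2 ties the routine scales to PHP instead: "On their first contact with PHP, all patients in Adult PHP complete various eating disorder indices", including the ED-15. It ties ABUSI and BIS/BAS to study enrollment.

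**Who qualifies.** Section 3.1 requires "Electing to participate in child or adult partial hospitalization program for eating disorder treatment at MSHMC". It does not require that the program has begun.

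**What is not stated.** No section limits the interval from intake to the first PHP day, says what happens to a randomized person who never attends, or defines an analysis set. Section 8.1 fixes 60 participants, 30 per arm. Section 3.3.2 says withdrawn subjects need not be replaced.

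**The concern.** Allocation and the baseline measurement of the primary outcome both depend on an event that the protocol dates in two ways. Under the intake route, a participant can complete the baseline ED-15 and be randomized before any PHP attendance. Under the PHP route, the same steps fall on the first program day. The reference point for weeks 1, 3 and 6 is then unclear: it could be enrollment, PHP start or first dose.

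Two things are at stake. First, change from baseline includes a pre-PHP interval for some participants and not for others. That adds variance to the arm comparison and shifts the within-group comparisons over time planned in section 8.3. Second, people who elect PHP but never start it can hold places in a fixed sample of 60, with no rule for replacing or analysing them.

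**Working it through.** The plan has no figure to reproduce. Sections 8.1 and 8.2 set 60 a priori, with no alpha, power, effect size, SD or dropout rate. The check therefore reads the sections side by side and then illustrates size under labelled assumptions.

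**1. Sections side by side.** Sections 4.2.3, 5.2.1 and 7.1.1 allow enrollment before or at PHP start. Study Procedures and Duration of Participation allow it only at PHP start. Both cannot govern. Under the first reading, section 7.3.3 puts randomization at medical intake, and section 3.1 is already met because PHP has been elected.

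**2. Interval from enrollment to dosing.** Study Procedures supplies study article after the urine drug screen and consent. For intake enrollees, section 7.1.1 allows seven days for outstanding routine labs and sets no limit on the wait for PHP. For PHP-day enrollees, it says routine labs are typically obtained at the first medical appointment, within the first seven days of programming. Either route can leave a gap before the first dose; the length differs and is not capped.

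**3. Non-starters.** Let f be the share of randomized people who never start PHP or study drug (assumed). At 5% the number is 0.05 × 60 = 3; at 10% it is 0.10 × 60 = 6.

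For scale, assume two-sided alpha 0.05 and 80% power at 30 per arm. The detectable difference is d = (1.960 + 0.842) × √(2/30) = 0.72 SD. Two ways of handling non-starters:

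- All randomized analysed, with no drug effect in non-starters: power = Φ(d(1−f)/√(2/30) − 1.960)
- Non-starters excluded: the same formula with undiluted d and n = 30(1−f) per arm

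| f (assumed) | All analysed, effect diluted | Excluded |
|---|---|---|
| 0% | 80% | 80% |
| 5% | 76% | 78% |
| 10% | 71% | 76% |
| 20% | 61% | 71% |

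**4. Mixed baseline timing.** Let p be the share enrolled early and s the resulting shift in their baseline ED-15, in SD units. Assume p = 0.2 to 0.5 and s = 0.2 to 0.5.

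- Expected between-arm difference from timing: zero, because arm is assigned at random.
- SD of the chance imbalance between arms, s√(2p(1−p)/30): 0.021 to 0.065.
- Variance multiplier, 1 + p(1−p)s²: 1.006 to 1.062, that is about 1% to 6% more variance. Power moves from 80% to between 78% and 80%.
- Shift in mean within-group change, p × s: 0.2 × 0.2 = 0.04 SD to 0.5 × 0.5 = 0.25 SD.

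A simulation of 20,000 trials at p = s = 0.5 gave a mean arm difference of −0.002 and a type I error of 5.1%, so it showed no bias.

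**The case against.** The strongest reply is that this is only a drafting inconsistency in a single-site pilot sized without a power calculation. Study Procedures and Duration of Participation already tie enrollment and the clock to PHP start. The schedule, as extracted, lists both initial assessments before enrollment, and randomization balances any mix of timing between arms. Much of this stands. It limits the point to precision, interpretation of within-group change, and wasted slots. It does not remove the intake route, which three sections allow, or supply a rule for non-starters.

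Four stronger readings are tempting but not supported:

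- A reader might infer that mixed baselines make the arms non-comparable. Step 4 shows no bias in expectation and a small loss of precision.
- A reader might infer that only intake enrollees wait between enrollment and dosing. Section 7.1.1 gives PHP-day enrollees up to a week for labs.
- A reader might infer that non-starters would have no week 3 or week 6 data. Surveys go out by emailed REDCap link, and section 7.3.2 plans off-site completion, although it writes this for people who finish PHP early. Non-starters may contribute little or nothing; the documents do not settle it.
- A reader might infer that non-starters certainly receive no study article. Study Procedures ties daily use to time in programming but supply only to the drug screen and consent, and section 7.3.2 lets treatment continue after PHP discharge. These statements need reconciling.

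**Conclusion.** The concern holds as an internal contradiction with consequences for design. Enrollment is dated in two ways, randomization and baseline follow it, and electing PHP is enough to enter. People who never start PHP can therefore be randomized, and the baseline ED-15 lacks a uniform relation to PHP start and first dose.

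Non-starters are the larger part of the cost. An assumed 5-10% is 3 to 6 of 60, and would take an illustrative 80% power to 71-76% if all randomized are analysed, or 76-78% if non-starters are excluded. Mixed timing costs about 1-6% in variance under the assumed ranges. It could move within-group change by 0.04 to 0.25 SD, which randomization does not correct because that comparison has no control arm.

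The non-start rate, the share enrolled at intake, the interval to PHP and the baseline shift are all assumptions; none is in the documents. A larger precision loss could be produced by supposing that the baseline to week 6 correlation falls from 0.6 to 0.5: (1 − 0.5²)/(1 − 0.6²) = 0.75/0.64, about 17% more residual variance. That requires the drop to apply to the whole sample, including people enrolled at PHP start, and a baseline-adjusted analysis that section 8.3 does not specify. It should not be relied on.

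**What to change.** Keep both consent opportunities and separate consent from time zero.

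- Reconcile sections 4.2.3, 5.2.1 and 7.1.1 with Study Procedures and Duration of Participation.
- In sections 7.1, 7.2 and 7.3.3, set one sequence for everyone: baseline ED-15, EDE-Q, PHQ-9, GAD-7, ABUSI and BIS/BAS, then REDCap randomization. Place it in a short stated window after PHP attendance has begun and the protocol's eligibility results are available, and before the first dose.
- Change the inclusion wording in section 3.1 from electing PHP to having started it.
- Count weeks 1, 3, 6 and 8-9 from that point.

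A window is needed rather than the first PHP day itself. Section 3.2 makes ALT/AST, the opioid screen and the serum pregnancy test exclusion criteria, and section 6.2.3 expects a negative drug screen and normal bloodwork before enrollment. Under section 7.1.1 those results may not exist on day one. Randomizing then could create the post-randomization exclusions that the change is meant to avoid.

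The cost is protocol wording and a change to REDCap timing. Adult PHP already collects the ED-15 at first PHP contact. The downsides are a short delay to randomization for some participants and less lead time for the pharmacy to deliver the first week's capsules.
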